| | 
 • Previous surgery in pelvis (e.g. bilateral hip replacement) that limit the extent of pelvic lymph node dissection • Patients who refuse radical prostatectomy or pelvic lymph node dissection • Patients who refuse to join the trial or are unable to consent • Patients not being considered for further therapy • Patient has absolute contra-indications to undergoing MRI scanning • Patients who cannot lie still for at least 60 to 75 minutes or comply with imaging • Subject has medical conditions that would limit study participation (per physician discretion) • Subject is enrolled in one or more concurrent studies that would confound the study results of this study as determined by the study investigators • Subject has a limited life expectancy that would not allow completion of the 24 month visits |
| STUDY PROCEDURES St Vincent's Hospital, Sydney | 
 1. Men diagnosed with prostate cancer are referred to a participating urologist for a radical prostatectomy 2. The patients are consented to the study by the urologist following fulfilment of the selection criteria 3. The patient is referred to the Department of Nuclear Medicine, St Vincent's Hospital, Sydney 4. The 68Ga-PSMA PET Scan is performed at the Department of Nuclear Medicine, St Vincent's Hospital, Sydney 5. On the return visit, "Combidex" is administered to the patient and the patient is referred to Medscan Barangaroo for a MRI scan 6. Radiologist and Urologist annotate suspect lymph nodes using the Pelvic Lymph Node Diagnostic Template and assign index of suspicion to each area 7. Patient undergoes radical prostatectomy including the removal of lymph nodes 7-10 days following Combidex nano-MRL 8. The prostate and the lymph nodes are sent to histology for reporting 9. Analysis: 
 a. Histology Vs Nano-MRL b. Histology Vs Ga68 PSMA PET c. Histology Vs Nano-MRL Vs Ga68 PSMA PET 10. Repeat Ga68 PSMA and Nano-MRL if not concordant with Histology within 6-8 weeks of surgery 11. Follow up Visits: The participant will have clinical follow up reviews as part of their care at 6 weeks, 2 months, 6 months, 12 months and 24 months 12. Participant will complete the Expanded Prostate Cancer Index Composite (EPIC) survey at baseline (prior to surgery), 6 weeks, 3 months, 6 months, 1 years and then yearly for a minimum of 5 years). |

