Intravenous Nano-MR, using dextran coated small iron oxide particles (ferumoxtran-10, Combidex®, Radboudumc, The Netherlands), allows detection of metastatic LN in even very small (>2 mm) LN [14-16]. Thus Nano-MR results in a significant improvement of the detection of LN metastases compared to other existing techniques [14-16]. For example, compared to 11C-Choline PET/CT, Nano-MR detected more metastatic LN (738 vs 132) in more patients (23/29 vs 13/29) in smaller LN (mean diameter 4.9 vs 8.4 mm)[18]. Nano-MR also obviates the use of surgical removal of LN [5, 16], and thereby reduces unnecessary side effects and decreases health care costs. A large prospective multi-centre study demonstrated the cost-effectiveness [10, 19]. Furthermore, with Nano-MR LN metastases are more accurately detected than with current nomograms [20, 21]. Nano-MR images can guide selective radiation of small, thus far undetected metastatic LN [12], and is expected to improve patient outcomes again [13, 22]. No prospective data is available comparing Nano-MR with 68Ga-PSMA.

History:

Approximately 15 years ago Nano MRI using Combidex became available for human use. The data from primary pharmacokinetic studies, a Phase I study and the data in a Phase II study were consistent, despite the different designs and rates of administration of the contrast agent. These studies showed:

1. A single intravenous dose of Combidex up to 1.7 mg Fe/kg is safe and tolerated. MRI results demonstrated the agent's ability to affect imaging characteristics of the blood pool, well-perfused organs, and cervical LN.
2. The Combidex doses of 1.1, 1.7, 2.6 and 3.4 mg Fe/kg could be safely administered. Signal intensity data and specificity rates for detecting normal LN demonstrated that the best imaging results were achieved with doses of 2.6 and 3.4 mg Fe/kg when MRIs were obtained 24 or 36 hours after Combidex administration. Because the results for those two doses and two imaging times were similar, the lower dose (2.6 mg Fe/kg) was chosen as the dose to be used in Phase III LN studies, with an imaging time of 24 to 36 hours. Pharmacokinetic results were similar to those from other studies, suggesting that the elimination of Combidex is unaffected by the rate of administration.

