3. The administration of Combidex at the doses proposed (1.1 and 2.6 mg Fe/kg) has no immediate or delayed effect on immune function. The pattern of immune cell activity in the Combidex groups was similar to that in the placebo group during 8 weeks of pre-dose evaluations and 6 months of post-dose evaluations.
4. The pharmacokinetics of Combidex were linear in the range of doses tested. The half-life is 25 to 30 hours. There were no differences between the sexes in any pharmacokinetic parameters. Signal intensity analyses showed that the maximum contrast effect of Combidex occurred immediately after dose administration for liver and spleen and 24 hours after administration for lymph nodes. Most of the changes in signal intensity disappeared from LN within 7 days after administration of the dose recommended for lymph node MRI (2.6 mg Fe/kg). Assays of serum ferritin showed that total body iron stores were elevated to maximum levels 72 hours after dose administration and then slowly returned to normal.

In the US, two attempts were made to register Combidex through the FDA for clinical lymph node imaging, two similar attempts were made by Guerbet in Europe (under sublicensing) by EMEA. All four attempts failed due to suboptimal trial design, suboptimal statistics, and suboptimal central reading of imaging studies.

Finally in December 2007 the last application was withdrawn. The CHMP (EMA) stated that, despite potential benefits and an acceptable safety profile; the pivotal study failed to demonstrate a consistent and statistically significant benefit for Combidex in sensitivity and failed to confirm non-inferiority with regards to specificity. All outstanding issues on quality, non-clinical documentation,

and clinical safety were, however, resolved before dossier withdrawal. A summary of the evaluation of the EMEA CHMP registration process, concerning the value and safety of Sinerem/Combixel is attached.

The Oncology Drugs Advisory Committee published a briefing document on Combixel in 2005 is attached. They concluded that Combixel could be safely administered by slow infusion over a period of approximately 30 minutes following dilution in 100 ml of normal saline. This method of administration minimizes adverse events and allows management of adverse events that may occur by stopping the infusion. The rate of serious events is less than a third of the rates experienced with iodinated contrast agents currently used with CT.

68Ga-PSMA PET Imaging:

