5. STUDY OUTLINE

5.1. STUDY FLOW CHART

5.2. INVESTIGATION PLAN

1. Screening Procedures

Participants will be screened when they attend their first urology consultation for a radical prostatectomy following the diagnosis of prostate cancer. The participant will be intermediate and high-risk cancer patients with a $\geq 10\%$ probability on LN where LND would currently be performed as part of the treatment protocol (guided by the updated Briganti nomogram) [34]. All patients will have a clinical work-up in line with the current international guidelines for the treatment of high-risk prostate cancer including a pelvic MRI and routine bone scan. They will be assessed against the inclusion and exclusion criteria. Should they be deemed eligible for the trial, they will be provided with details of the trial and will be asked to participate by providing written consent.

2. Imaging

Participants who have consented to participate will then be referred to the St Vincent's Nuclear Medicine Department will have the following imaging services prior to surgery:

- 68Ga-PSMA PET scan
- Diagnostic CT (part of the 68Ga-PSMA PET scan)

In the event that a participant had a clinically indicated 68Ga-PSMA PET scan within 3 weeks at St Vincent's Hospital, the participant will not be required to have another scan. If the 68Ga-PSMA PET scan was performed elsewhere, the participant will be required to have one performed at St Vincent's Hospital for consistent reporting. The 68Ga-PSMA PET scan will be double assessed by two experienced readers at St Vincent's Hospital, Sydney and the Wesley Hospital.

At the return visit and prior to the surgery, Combidex, the imaging agent, will be administered to the patient at St Vincent's Hospital, Sydney. Combidex will be administered by a trained member of staff. Combidex will be administered by slow infusion over approximately 30 minutes following dilution in 100mls of normal saline. This method of administration minimises adverse events and allows the management of adverse should they occur by the halting the infusion. The protocol for Combidex Nano MRL infusion is found appendix C.

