Following the infusion, the participants will be observed for one hour before being allowed to return home. The risk management of the infusion are described in item 5.3. In the next 2 to 3 days, the participants will be referred to have a MRI at Medscan Bangaroo. All Nano MRL scans will be double assessed by two experienced readers (one at I-Med Radiology and the other at The Wesley Hospital) and then by an experienced reader of Radboud University Nijmegen, the Netherlands.

The assessment of Nano MRL and 68Ga-PSMA PET scans represents a crucial endpoint in this study. Consequently, before the start of the trial we will define imaging standards and provide an intensive training of image interpretation. In order to ensure a homogeneous high quality of image assessment according to the requirements of MAGNIFI Trial, extensive effort will be made for training, including a 10 days training at the Radboud University Nijmegen the Netherlands. To assure the quality of this training, each investigator judging the images in the MAGNIFI Trial will have to pass a certification.

3. *Radical prostatectomy with pelvic lymph node dissection*

Patients will undergo radical prostatectomy and extended pelvic lymph node dissection, as clinically indicated within 7-10 days following Combidex nano-MRL imaging, with all dissected lymph node packets being dissected and labelled. Suspicious lymph nodes detected on nano-MRL or PSMA will be specifically targeted for resection during lymph node dissection.

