Appendix C: Protocol Infusion “Combidex” Nano MRL Version 1.0 29th Sept 2015

Protocol Infusion “Combidex” Nano MRL Version 1.0 29th Sept 2015

To perform a MRI NANO scan, infusion of NANO contrast fluid (Combidex) is required (Iron-Dextran nanoparticles 20mg/ml). The contrast fluid should be administered 24 to 36 hours before the MRI scan, by intravenous infusion that will take at least 30 minutes for administration. In this protocol we describe how the NANO contrast fluid should be prepared and administered.

Equipment Required:

| Material | Quantity |
|--|----------------------------|
| Drawing up equipment (10ml syringe, 18g needles x 2) | 1x |
| Sodium Chloride 0.9% | 2x 100ml |
| Cannulation equipment | 1x |
| Intravenous Giving Set | 1x |
| Intravenous Infusion Pomp | 1x |
| Iron-Dextran nanoparticles 200mg Iron = 10ml (20mg/ml) (NANO contrast fluid “Combidex”) | Based on total body weight |
| Filter 0.22 µm | 1x |
| Alcohol Swabs | 1x |

Dose table. The dose of Iron-Dextran Nanoparticles 20mg/ml is based on body weight = 0.13 ml per kg.

| Kg | Dose | Kg | Dose | Kg | Dose | Kg | Dose |
|----|------|----|------|-----|------|-----|------|
| 40 | 5,2 | 63 | 8,2 | 86 | 11,2 | 109 | 14,2 |
| 41 | 5,3 | 64 | 8,3 | 87 | 11,3 | 110 | 14,3 |
| 42 | 5,5 | 65 | 8,5 | 88 | 11,4 | 111 | 14,4 |
| 43 | 5,6 | 66 | 8,6 | 89 | 11,6 | 112 | 14,6 |
| 44 | 5,7 | 67 | 8,7 | 90 | 11,7 | 113 | 14,7 |
| 45 | 5,9 | 68 | 8,8 | 91 | 11,8 | 114 | 14,8 |
| 46 | 6,0 | 69 | 9,0 | 92 | 12,0 | 115 | 15,0 |
| 47 | 6,1 | 70 | 9,1 | 93 | 12,1 | 116 | 15,1 |
| 48 | 6,2 | 71 | 9,2 | 94 | 12,2 | 117 | 15,2 |
| 49 | 6,4 | 72 | 9,4 | 95 | 12,4 | 118 | 15,3 |
| 50 | 6,5 | 73 | 9,5 | 96 | 12,5 | 119 | 15,5 |
| 51 | 6,6 | 74 | 9,6 | 97 | 12,6 | 120 | 15,6 |
| 52 | 6,8 | 75 | 9,8 | 98 | 12,7 | 121 | 15,7 |
| 53 | 6,9 | 76 | 9,9 | 99 | 12,9 | 122 | 15,9 |
| 54 | 7,0 | 77 | 10,0 | 100 | 13,0 | 123 | 16,0 |
| 55 | 7,2 | 78 | 10,1 | 101 | 13,1 | 124 | 16,1 |
| 56 | 7,3 | 79 | 10,3 | 102 | 13,3 | 125 | 16,3 |
| 57 | 7,4 | 80 | 10,4 | 103 | 13,4 | 126 | 16,4 |
| 58 | 7,5 | 81 | 10,5 | 104 | 13,5 | 127 | 16,5 |
| 59 | 7,7 | 82 | 10,7 | 105 | 13,7 | 128 | 16,6 |
| 60 | 7,8 | 83 | 10,8 | 106 | 13,8 | 129 | 16,8 |
| 61 | 7,9 | 84 | 10,9 | 107 | 13,9 | 130 | 16,9 |
| 62 | 8,1 | 85 | 11,1 | 108 | 14,0 | 131 | 17,0 |

Preparation:

1. Ensure there is a current valid prescription.
2. Make an infusion system and 100ml 0.9% Sodium Chloride.

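### Section 5.2 allows the Nano-MRL scan up to 2 to 3 days after Combidex, but the infusion protocol it cites (Appendix C) sets 24 to 36 hours

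*Protocol*

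**What the plan says.** Section 5.2 (Investigation plan, item 2, Imaging) has Combidex given at a return visit before surgery and refers the reader to the appendix: "The protocol for Combidex Nano MRL infusion is found appendix C". After the one-hour observation period it continues: "In the next 2 to 3 days, the participants will be referred to have a MRI at Medscan Bangaroo".

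Appendix C opens with a different interval: "The contrast fluid should be administered 24 to 36 hours before the MRI scan".

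The synopsis (Study procedures, step 5) says only that "the patient is referred to Medscan Barangaroo for a MRI scan" and gives no time.

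Section 1.1 gives the history of the agent. It says that 2.6 mg Fe/kg was "chosen as the dose to be used in Phase III LN studies, with an imaging time of 24 to 36 hours". It also puts the peak contrast effect in lymph nodes at 24 hours and adds: "Most of the changes in signal intensity disappeared from LN within 7 days after administration of the dose recommended for lymph node MRI".

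On infusion duration, section 5.2 states: "Combidex will be administered by slow infusion over approximately 30 minutes". Section 5.3, citing the manufacturer, and Appendix C both set 30 minutes as a minimum.

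**The concern.** Nano-MRL is one of the two index tests, and its comparison with histology is part of the primary objective (section 2.1). It also enters the imaging consensus in section 7, where a packet counts as positive if either test is positive. When the scan is taken relative to the infusion is therefore part of the definition of the test being evaluated.

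Staff who book from section 5.2 can scan outside the interval set by the trial's own infusion protocol. The reported accuracy would then describe a mixture of acquisition times, or a later acquisition, and not the technique as specified. By the protocol's own account, nodal signal changes with time after dosing, so the interval cannot be treated as incidental.

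**Working it through.** No sample-size or power figure is involved. The check sets the stated windows side by side in hours.

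**Inputs**

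| Source | Interval from infusion to scan |
|---|---|
| Section 5.2, item 2 | 2 to 3 days |
| Appendix C, opening paragraph | 24 to 36 h |
| Section 1.1, imaging time chosen for Phase III | 24 to 36 h, at 2.6 mg Fe/kg |
| Synopsis, step 5 | none stated |

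**Step 1. Conversion.** 2 × 24 = 48 h and 3 × 24 = 72 h.

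**Step 2. Section 5.2 read as a window of 48 to 72 h.** Appendix C closes at 36 h. The earliest scan is 48 − 36 = 12 h late and the latest is 72 − 36 = 36 h late. The windows do not overlap.

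**Step 3. Section 5.2 read as within 2 to 3 days.** The permitted range now contains 24 to 36 h, so one scan time can satisfy both texts. Scans up to 12 h late (2-day limit) or 36 h late (3-day limit) are still permitted, as are scans earlier than 24 h.

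**Step 4. Section 5.2 read as timing the referral only.** Section 5.2 then sets no scan time. A referral made on day 2 or 3 would itself come after the 36 h limit.

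**Step 5. Does the background interval apply to the dose used here?** Appendix C states: "The dose of Iron-Dextran Nanoparticles 20mg/ml is based on body weight = 0.13 ml per kg". So 0.13 ml/kg × 20 mg/ml = 2.6 mg Fe/kg. The dose table agrees: a 70 kg man receives 9.1 ml, and 9.1 × 20 / 70 = 2.6 mg Fe/kg. This is the dose for which section 1.1 reports the 24 to 36 h imaging time. The background sets no rule for this trial, but it supports the Appendix C window and not the one in section 5.2.

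**Step 6. What cannot be computed.** Section 1.1 gives the nodal peak (24 h) and the time by which most of the signal change has gone (7 days). It gives no signal or accuracy results between 36 and 72 h. The half-life of 25 to 30 h quoted there is for the agent, not for nodal contrast, so it cannot be converted into lost sensitivity or specificity. How many of the 120 men would be affected depends on how staff read the sentence.

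**The case against.** The strongest reply is that the sentence in section 5.2 is a loose outline and that its ordinary meaning is within 2 to 3 days. It speaks of referral, and the same section sends staff to Appendix C for the operating detail. Read together, the specific document narrows the general sentence, and a scan at 24 to 36 h satisfies both. The protocol also promises defined imaging standards before the start (section 5.2) and training at Nijmegen in Combidex injection and Nano-MRL reading (section 5.3). No harm to accuracy is demonstrated.

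Part of this stands. A reading exists under which both instructions can be met, and no bias can be claimed. But no reading confines section 5.2 to 24 to 36 h, and neither the imaging standards nor the training text states a scan window.

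Three smaller objections are fair. Appendix C (Administration, step 4) already has the radiologist record the date and time the infusion starts, so only part of the timing data would be new. An analysis excluding out-of-window scans may properly sit in the statistical analysis plan, which is not at hand. Infusion duration is a separate matter from the scan interval, and section 5.3 and Appendix C already state the minimum; it is raised here only because it is the same kind of mismatch in the same part of section 5.2.

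**Conclusion.** The inconsistency is real and should be fixed. Section 5.2 permits Nano-MRL scans up to 36 h after the Appendix C window closes. On the 48 to 72 h reading it requires every scan to be 12 to 36 h late. The only assumption is that a day means 24 hours.

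The conclusion is limited to the acquisition rule for an index test in the primary objective. It makes no claim about the size or direction of any effect on accuracy, or about the number of men affected, because the protocol contains nothing from which either could be derived.

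As a secondary point, approximately 30 minutes in section 5.2 would allow a slightly shorter infusion than the minimum set in section 5.3 and Appendix C. Section 5.3 links the one reported death to rapid infusion, so the wording should match.

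**What to change.** - In section 5.2, state that the MRI is performed 24 to 36 hours after the Combidex infusion, as in Appendix C. Say whether the interval runs from the start or the end of the infusion. If scheduling needs a longer window, justify it and amend Appendix C to match.
- Record the infusion-end and scan-start times for each man, alongside the start time that Appendix C already requires.
- Report Nano-MRL and consensus accuracy with out-of-window scans excluded as a sensitivity analysis. The detail can go in the statistical analysis plan.
- In section 5.2, change the infusion time to at least 30 minutes.

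The cost is two wording changes and at most two time fields on the case report form. Scan booking becomes slightly less flexible. The sample size does not change.

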After all imaging is complete, Patients will undergo radical prostatectomy and extended pelvic lymph node dissection, as clinically indicated, with all dissected lymph node packets being dissected and labelled. Approximately 6 packets of lymph nodes are expected per patients, each hemipelvis providing node packets from the external iliac vein, obturator fossa and internal iliac vessels as described by Bader et al. Specifically, all fibro-fatty tissue along the external iliac vein along the pelvic sidewall, caudal to the femoral canal and proximally to the bifurcation of the common iliac artery will be dissected and removed to be labelled as 'external iliac vein nodal packet'. All fibro-fatty tissue within the obturator fossa along the obturator muscle, skeletonising the obturator nerve and vessels will be labelled 'obturator fossa'. Finally the internal iliac artery and internal iliac vein will be skeletonised, all tissue removed from this dissection will be labelled 'internal iliac vessels'. Suspicious lymph nodes detected on nano-MRL or PSMA will be additionally targeted for resection during lymph node dissection, particularly presacral and mesorectal nodes. Specifically identified nodes in the mesorectal plane may be localised with percutaneous hookwire prior to dissection. At the discretion of the operating surgeons, and in consultation, suspicious nodes outside this template may also be resected if doing so does not place the patient at significant additional risk. Each nodal packet removed will also be qualified as either 'complete' or 'incomplete' for imaging vs histology concordance analysis. The reason for 'incomplete' dissection will be recorded.

An accredited robotic urological surgeon will perform the pelvic lymph node dissection. All participating urologists will undergo external video analysis and independent validation prior to commencement of the MAGNIFI trial.

4. *Histopathology*

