After dissection, the specimens will be sent to pathology for histopathological examination. The lymph nodes will be reviewed at 2mm dissections. The result of histological examination of the lymph nodes (gold standard) will be compared with the result of 68Ga-PSMA PET scan and Nano MRL. Sensitivity, specificity, positive predictive value (PPV), and negative predictive value (NPV) for Nano MRL and Ga68-PSMA PET scan in pelvic lymph nodes with corresponding CT size measurement in comparison with histopathology will be assessed for detection of lymph node metastases.

Analysis will include assessing sensitivity, specificity, diagnostic accuracy, positive and negative predictive values for different levels of Nano MRL and PSMA PET avidity in pelvic lymph nodes with corresponding CT size measurement in comparison with histopathology.

5. *Re-imaging*

In participants where the 68Ga-PSMA PET and/or Nano MRL detected metastases in the lymph nodes but these were not seen in the histopathology (i.e., a false positive result), the participant will undergo a repeat PSA test, a 68Ga PSMA PET scan and a Nano MRL 6 weeks after the radical prostatectomy to confirm the accuracy of the original results and to ensure that no other sites of metastases missed. As noted in section 5.3, correspondence from [name] (Appendix D) and from clinical evidence to date, there have been no safety issues as a consequence of having a repeat 68Ga PSMA PET scan and/or a Nano MRL. All precautionary safety measures will be performed.

6. Follow up visits

As part of the participant's clinical care, follow up consultations with the treating urologist are planned for 6 weeks, 2 months, 6 months, 12 months and 24 months post surgery.

7. Quality of Life (QOL) survey

To determine the outcome of treatment, the participant will be asked to complete the self-reporting Expanded Prostate Cancer Index Composite (EPIC) survey. The EPIC survey has been extensively used to report on the physical, emotional and psychological outcomes of the prostate cancer patients. The participant will ask to complete the survey at baseline (prior to surgery), at 6 weeks, 3 months, 6 months, 1 year and then yearly for a minimum of 5 years.

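### The protocol does not require pathology to be masked to the scans, and specimens removed only because imaging flagged them disclose a positive scan, so sensitivity may be overstated

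*Protocol*

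**What the plan says.** Protocol section 5.2, item 4 (Histopathology) makes histology the comparator for both scans: "The result of histological examination of the lymph nodes (gold standard) will be compared with the result of 68Ga-PSMA PET scan and Nano MRL". How that comparator is produced is described only by the statement that "the specimens will be sent to pathology for histopathological examination. The lymph nodes will be reviewed at 2mm dissections". The item does not say what the pathologist may be told, what goes on the request form, or whether a result can be revised once imaging is known.

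The surgical side knows the imaging by design. In the synopsis (Study procedures, step 6), "Radiologist and Urologist annotate suspect lymph nodes using the Pelvic Lymph Node Diagnostic Template and assign index of suspicion to each area". Section 5.2, item 3 then lets imaging direct the resection:

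- "Suspicious lymph nodes detected on nano-MRL or PSMA will be specifically targeted for resection during lymph node dissection".
- Such nodes "will be additionally targeted for resection during lymph node dissection, particularly presacral and mesorectal nodes".
- A hookwire may be placed beforehand to mark scan-identified nodes in the mesorectum.
- At the surgeons' discretion, "suspicious nodes outside this template may also be resected if doing so does not place the patient at significant additional risk".

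The same item also describes three routine packets per side, six per patient. All the tissue in these regions is taken whatever the scans show, and each packet is labelled by its anatomical region. The sample size in section 7(a) and the a-to-f packet table in section 7(b) rest on six packets per patient. Section 7 does not say whether specimens from outside those regions enter the analysis.

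**The concern.** Two mechanisms can favour imaging.

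The first is disclosure and selection. A presacral, mesorectal or off-template specimen reaches pathology because a scan was positive, so its site tells the reader the index result. Sites that were not flagged are not removed from these areas. Such specimens can therefore add scan-positive results to the accuracy table but no scan-negative ones.

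The second is uneven search. For the six routine packets, nothing stops the scan result or the annotated template from travelling with the specimen. A pathologist who knows that a packet was flagged may look harder for a small deposit there than in an unflagged packet. Deposits missed in unflagged packets would then not be balanced by similar misses in flagged ones, and sensitivity would read too high.

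Sensitivity matters here because the hypothesis in section 2 would spare men a dissection on the strength of a negative combined assessment. What the reference reader sees is settled when the specimens are read, so an analysis plan cannot repair it later.

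**Working it through.** **Inputs.** The planning table in section 7(a), as proportions of packets: scan+/histology+ 0.12, scan+/histology- 0.07, scan-/histology+ 0.03, scan-/histology- 0.78. It agrees with the stated inputs: prevalence 0.12 + 0.03 = 0.15; discordance 0.07 + 0.03 = 0.10; difference 0.07 - 0.03 = 0.04. It implies:

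- sensitivity 0.12/0.15 = 80.0%
- specificity 0.78/0.85 = 91.8%
- PPV 0.12/0.19 = 63.2%
- NPV 0.78/0.81 = 96.3%

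**Uneven search in routine packets.** Take the planning table as the truth. Let routine review miss a share m of truly positive packets. The range m = 5-20% is an assumption, since the documents give no miss rate. No false calls of metastasis are assumed.

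*Even search* (every packet misses m):
- sensitivity = 0.12(1-m)/[0.15(1-m)] = 0.80
- PPV = 0.12(1-m)/0.19
- specificity = (0.78+0.03m)/(0.85+0.15m)
- NPV = (0.78+0.03m)/0.81

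*Uneven search* (flagged packets miss nothing, unflagged packets miss m):
- sensitivity = 0.12/[0.12+0.03(1-m)]
- PPV = 0.12/0.19
- specificity = (0.78+0.03m)/(0.85+0.03m)
- NPV = (0.78+0.03m)/0.81

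| m | Sensitivity even / uneven | PPV even / uneven | Specificity even / uneven | NPV, both |
|---|---|---|---|---|
| 5% | 80.0 / 80.8 | 60.0 / 63.2 | 91.1 / 91.8 | 96.5 |
| 10% | 80.0 / 81.6 | 56.8 / 63.2 | 90.5 / 91.8 | 96.7 |
| 20% | 80.0 / 83.3 | 50.5 / 63.2 | 89.3 / 91.8 | 97.0 |

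Uneven search moves sensitivity above its true value by 0.8 to 3.3 points. PPV equals the planning value, and specificity equals it to rounding. NPV is identical under the two searches, because unflagged packets are searched in the same way in both.

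Section 7(a) also mentions 95% sensitivity. On that figure the uneven read would be 0.95/[0.95+0.05(1-m)]: 0.95/0.9975 = 95.2% at m = 5% and 0.95/0.99 = 96.0% at m = 20%. The shift is smaller when there are fewer false negatives to miss.

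**Pooling imaging-directed specimens.** Section 7(b) calls the combined evaluation positive if either scan is positive. A specimen removed because a scan flagged it is therefore always positive on the combined evaluation. Per routine packet, let a be the number of such specimens with metastasis and b the number without. After pooling:

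- sensitivity = (0.12+a)/(0.15+a) = 1 - 0.03/(0.15+a), which exceeds 0.80 for any a > 0
- specificity = 0.78/(0.85+b), which falls for any b > 0

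The documents give neither a nor b, so this shift has a direction but no computable size. For a single modality the effect is mixed: a node flagged only by the other scan enters that modality's table as a false or true negative.

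**The case against.** The strongest objection is that the protocol is silent on masking rather than opposed to it. A reader might infer that the read is unmasked, or that the plan hands the scan result to pathology. The documents do not support that: the annotated template belongs to the radiologist and urologist, nothing routes it to the pathologist, and a pathology request form may exist that is not shown. This stands. The gap is a missing requirement.

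A reader might also infer that targeted resection unmasks the whole packet analysis. It does not. The six routine packets are taken regardless of the scan and labelled by region. Disclosure by site is confined to the additional specimens, whose number is not given.

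Harder searching of flagged tissue is also nowhere prescribed. The 2 mm review applies to all nodes alike. Imaging-positive, histology-negative cases lead to repeat PSA and scans, and no second pathology search is written. So uneven search is a risk, not a planned step.

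Finally, one might claim that PPV and specificity are inflated too, since they read higher than under an even search (63.2% against 60.0-50.5%; 91.8% against 91.1-89.3%). In this model the extra deposits found are real, so these values return to the planning figures and do not exceed them. Nor does uneven search distort NPV, the measure closest to omitting dissection: both searches give 96.5-97.0%.

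What remains is that masking is not required, that imaging-directed specimens do disclose their scan status, and that both routes push sensitivity upwards.

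**Conclusion.** The point holds in a limited form. The protocol does not protect the reference read from knowledge of the scans, and it creates a set of specimens that disclose a positive scan and cannot be false negatives for the combined evaluation. Pooling those specimens with the routine packets can raise sensitivity by an amount the documents do not allow one to compute. In the routine packets, uneven search would make sensitivity read about 80.8-83.3% instead of 80%. That rests on the planning table, an assumed 5-20% routine miss rate, and complete detection in flagged packets. NPV is the same under both searches, and PPV and specificity are not pushed above the planning values.

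The shift is modest beside sampling error. With 0.15 × 720 = 108 positive packets, the 95% half-width for a sensitivity of 80% is 1.96 × √(0.8 × 0.2/108) = 7.5 points without clustering. Dividing 108 by the protocol's inflation factor of 2.5 gives 43.2 and a half-width of 11.9 points. But this bias does not shrink with recruitment, and it costs little to prevent. The change is a worthwhile improvement; the point does not show that the trial's accuracy results will be wrong.

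**What to change.** Amend section 5.2, item 4 as follows:

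- Send packets to pathology under anatomical site and side only, with no scan result and no annotated template on the request form.
- Apply the same 2 mm sectioning to every packet.
- Have the pathologist record and date the packet-level result before seeing any imaging, and use that result in the primary analysis.
- Record any later re-read prompted by imaging as a separate result that does not replace the first.
- Report imaging-directed off-template specimens, which cannot be masked, separately from the six routine packets.

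The cost is a change to the request form and one dated field on the pathology form. No extra reader is needed, and the same pathologist may use the imaging afterwards for the clinical report. The small downside is that the pathologist sees the imaging only after the first read.
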